8.3. Adverse Events and Serious Adverse Events

The definitions of an AE or SAE can be found in [Appendix 6](#). As described in [Appendix 6](#), intensity of AEs (and laboratory abnormalities) will be graded using the most recent version of the Division of AIDS (DAIDS) grading table at the time of the last participant last visit. While the study population will consist of HIV-1 seronegative healthy participants, the DAIDS criteria will be used in later phase clinical studies (Phase 2a and beyond); additionally, the DAIDS criteria have a more conservative grading scale relative to other scales (e.g., Common Terminology Criteria for Adverse Events [CTCAE] v 5.0). Thus, participant safety evaluation and monitoring will be more conservative.

The investigator and any qualified designees are responsible for detecting, documenting, and reporting events that meet the definition of an AE or SAE and remain responsible for following up AEs that are serious, considered related to the study intervention or the study, or that caused the participant to discontinue the study (see [Section 7](#)).

8.3.1. Time Period and Frequency for Collecting AE and SAE Information

- All SAEs will be collected from the signing of the ICF until the end of the study at the time points specified in the SoA ([Section 1.3](#)).
- All AEs will be collected from the start of intervention until the end of the study at the time points specified in the SoA ([Section 1.3](#)).
- Medical occurrences that begin before the start of study intervention but after obtaining informed consent will be considered medical history, not an AE, and will be recorded in the source documents.
- All SAEs will be recorded and reported to the sponsor or designee immediately and under no circumstance should this exceed 24 hours, as indicated in [Appendix 6](#). The investigator will submit any updated SAE data to the sponsor within 24 hours of it being available.
- Investigators are not obligated to actively seek AEs or SAEs after the conclusion of the study participation. However, if the investigator learns of any SAE, including a death, at any time after a participant has been discharged from the study, and he/she considers the event to be reasonably related to the study intervention or study participation, the investigator must promptly notify the sponsor.

8.3.2. Method of Detecting AEs and SAEs

- The method of recording, evaluating, and assessing causality of AEs and SAEs and the procedures for completing and transmitting SAE reports are provided in [Appendix 6](#).
- Care will be taken not to introduce bias when detecting AE and/or SAE. Open-ended and non-leading verbal questioning of the participant is the preferred method to inquire about AE occurrence.

8.3.3. Follow-up of AEs and SAEs

After the initial AE/SAE report, the investigator is required to proactively follow each participant at subsequent visits/contacts. All SAEs will be followed until the event is resolved, stabilized, otherwise explained, or the participant is lost to follow-up (as defined in Section 7.3). Further information on follow-up procedures is given in [Appendix 6](#).

8.3.4. Regulatory Reporting Requirements for SAEs

- Prompt notification by the investigator to the sponsor of a SAE is essential so that legal obligations and ethical responsibilities towards the safety of participants and the safety of a study intervention under clinical investigation are met.
- The sponsor has a legal responsibility to notify both the local regulatory authority and other regulatory agencies about the safety of a study intervention under clinical investigation. The sponsor will comply with country-specific regulatory requirements relating to safety reporting to the regulatory authority, Institutional Review Board (IRB) / Independent Ethics Committee (IEC), and investigators.
- Investigator safety reports must be prepared for suspected unexpected serious adverse reactions (SUSARs) according to local regulatory requirements and sponsor policy and forwarded to investigators as necessary.
- An investigator who receives an investigator safety report describing a SAE or other specific safety information (e.g., summary or listing of SAEs) from the sponsor will review and then file it along with the CIB and will notify the IRB/IEC, if appropriate according to local requirements.

8.3.5. Pregnancy

- Details of all pregnancies in female participants will be collected after the start of study intervention and through the end of pregnancy (termination or delivery).
- If a pregnancy is reported, the investigator should inform VH/GSK within 24 hours of learning of the pregnancy.
- Abnormal pregnancy outcomes (e.g., spontaneous abortion, fetal death, stillbirth, congenital anomalies, ectopic pregnancy) are considered SAEs.

8.3.6. Adverse Events of Special Interest

Adverse events of special interest include all AEs classified in the cardiovascular (per MedDRA) system organ class, seizure, and syncope. Additional AEs of special interest within other SOC (e.g., GI, Neurologic, and Psychiatric) may be defined in the Reporting and Analysis Plan.

8.4. Treatment of Overdose

For this study, any dose of GSK3640254 greater than the planned dose within a 24-hour time period (± 2 hours) will be considered an overdose.

VH/GSK does not recommend specific treatment for an overdose. The investigator will use clinical judgment to treat an overdose.

In the event of an overdose, the investigator should:

1. Contact the medical monitor immediately.
2. Closely monitor the participant for AE/SAE and laboratory abnormalities until GSK3640254 can no longer be detected systemically (at least 5 days).
3. Obtain a plasma sample for PK analysis immediately and through 7 days after the date of the last dose of study intervention if requested by the medical monitor (determined on a case-by-case basis).
4. Document the quantity of the excess dose as well as the duration of the overdosing in the CRF.

Decisions regarding dose interruptions or modifications will be made by the investigator in consultation with the medical monitor based on the clinical evaluation of the participant.

8.5. Pharmacokinetics

- Whole blood samples of approximately 2 mL will be collected for measurement of plasma concentrations of GSK3640254 as specified in the SoA (Section 1.3).
- A maximum of 10 samples may be collected at additional time points during the study if warranted and agreed upon between the investigator and the sponsor. Instructions for the collection and handling of biological samples will be provided by the sponsor. The actual date and time (24-hour clock time) of each sample will be recorded.
- Samples will be used to evaluate the PK of GSK3640254. Samples collected for analyses of GSK3640254 plasma concentration may also be used to evaluate safety aspects related to concerns arising during or after the study.
- Once the plasma has been analyzed for GSK3640254, any remaining plasma may be analyzed for other compound-related metabolites and the results reported under a separate protocol.

8.6. Pharmacodynamics

Pharmacodynamic parameters are not evaluated in this study.

8.7. Genetics

A 6-mL blood sample for DNA isolation will be collected from participants who have consented to participate in the genetics analysis component of the study. Participation is

optional. Participants who do not wish to participate in the genetic research may still participate in the study.

In the event of DNA extraction failure, a replacement genetic blood sample may be requested from the participant. Signed informed consent will be required to obtain a replacement sample unless it was included in the original consent.

See [Appendix 7](#) for information regarding genetic research. Details on processes for collection, shipment, and destruction of these samples can be found in the SRM.

8.8. Biomarkers

Biomarkers are not evaluated in this study.

8.9. Medical Resource Utilization and Health Economics

Medical resource utilization and health economics parameters are not evaluated in this study.

9. STATISTICAL CONSIDERATIONS

9.1. Statistical Hypotheses

There is no formal hypothesis that will be statistically tested in this study, the sample size is not selected based on statistical considerations but was determined using feasibility. For Part 1, a total of approximately 18 participants will be enrolled to ensure that 14 evaluable subjects complete Part 1. For Part 2, a total of approximately 21 participants will be enrolled to ensure that 16 evaluable subjects complete Part 2.

9.2. Sample Size Determination

9.2.1. Sample Size Assumptions

Based on the results from previous PK studies for GSK3640254 (GSK Studies 207187 and 208131) the intra-subject coefficient of variability (CV_w) ranged from 17% to 38% and 13% to 31%, respectively for AUC(0- τ) and C_{max}, respectively. For recent PK Study 209712 the CV_w was 7.8% and 11.5%, for AUC(0- τ) and C_{max}, respectively. Therefore, it is decided that 38% would be a conservative estimate on which the sample size calculation is based.

Administration of GSK3640254 mesylate salt tablet formulation may change the exposure to GSK3640254 from the capsule formulation; therefore, a range for point estimates (PEs) of 0.9, 1.0, and 1.1 was explored.

Administration of GSK3640254 with a high fat meal compared to fasting is expected to increase the exposure to GSK3640254; therefore, a range for PE of 1.0, 1.1, and 1.2 was explored.

For GSK3640254, with a sample size of 14 evaluable subjects in Part 1 and a sample size of 16 evaluable subjects in Part 2, it is estimated that the precision (i.e. half-width of the 90% CI on the log and ratio scales), and CI on the original scale for each PE will be:

Comparison	CVw (%)	Half-Width (log scale)	Half-Width (original scale)	Point Estimate	90% CI
GSK3640254 tablet to capsule	38	0.246	0.279	0.9	(0.704, 1.151)
				1.0	(0.782, 1.279)
				1.1	(0.860, 1.407)
GSK3640254 high fat to fasted	38	0.236	0.266	1.0	(0.797, 1.255)
				1.1	(0.877, 1.380)
				1.2	(0.956, 1.506)

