2. INTRODUCTION

2.1. Study Rationale

This is a Phase 1, 2-part, randomized, open-label, single-dose, crossover study to compare the relative bioavailability (BA) of the GSK3640254 formulation planned for Phase 2b (mesylate salt in a tablet) with the Phase 2a formulation (mesylate salt in a capsule) when administered following a moderate calorie and fat meal. Data from this study will determine whether dose adjustments are required due to formulation changes when transitioning from Phase 2a to Phase 2b clinical studies.

In addition, this study will investigate the effect of food on the pharmacokinetics (PK) of the GSK3640254 mesylate tablet formulation. All GSK3640254 completed clinical studies to date, including a Phase 2a (Part 1) proof of concept study, have been conducted with moderate calorie and fat meals. It is intended that this will be the only food-effect BA clinical study for GSK3640254; therefore, this study will investigate the effect of moderate and high calorie and fat meals on the PK, safety, and tolerability of the GSK3640254 mesylate tablet formulation, in comparison with administration under fasting conditions.

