2.2.3. Safety and Pharmacokinetic Data in Study 208131

The FTIH Study 207187 used a bis-hydrochloride salt capsule formulation of GSK3640254, which is not suitable for long-term clinical development.

Study 208131 was a single-center, open-label, 2-period, 2-sequence crossover design, conducted in 14 healthy participants in the United Kingdom. This study was designed to assess the relative BA of the formulation planned for Phase 2a (mesylate salt in a capsule) to the FTIH formulation (bis-hydrochloride salt in a capsule) administered following a moderate calorie and fat meal. All participants completed dosing and the safety data showed a total of 11 AEs (all Grade 1). Two AEs of headache were related to study drug. The most common AE was headache (3 instances). There were 3 GI AEs (abdominal pain, bleeding gums, and flatulence). There were no cardiac or psychiatric AEs. There were no clinically significant changes in vital signs, ECG parameters, or safety laboratory parameters.

Pharmacokinetic results from Study 208131 showed that in the presence of a moderate fat meal, the relative BA of GSK3640254 following 200 mg GSK3640254 mesylate salt administration relative to 200 mg GSK3640254 bis-hydrochloride salt administration was 112% and 116% based on AUC(0-t) and Cmax, respectively.

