4.2. Scientific Rationale for Study Design

This is a Phase 1, 2-part, randomized, open-label, single-dose, crossover study to compare the relative BA of the GSK3640254 formulation planned for Phase 2b (mesylate salt in a tablet) with the Phase 2a formulation (mesylate salt in a capsule) when administered following a moderate calorie and fat meal (Part 1). In addition, this study will investigate the effect of food on the PK of the GSK3640254 mesylate tablet formulation (Part 2).

The effect of food on the PK of a structurally similar HIV-1 MI (GSK3532795) was previously evaluated: AUC increased 1.8-, 2.1-, and 2.5-fold when a single dose of 180 mg GSK3532795 was given with a light, moderate, or high fat meal, respectively, as compared to administration under fasting conditions [GSK Document Number [2017N322200_00](#)]. All GSK3640254 completed clinical studies to date, including a Phase 2a (Part 1) proof of concept study, have been conducted with moderate calorie and fat meals. It is intended that this will be the only food-effect BA clinical study for GSK3640254; therefore, Part 2 of this study will investigate the effect of moderate and high calorie and fat meals on the PK, safety, and tolerability of the GSK3640254 mesylate tablet formulation, as compared with administration under fasting conditions.

The open-label crossover design of this study is well-established for evaluation of the relative BA of different oral dosage forms and for studying the effect of food on BA. Random assignment to treatment sequences is an attempt to prevent bias. The washout of at least 7 days between each dose of study intervention should eliminate the possibility of carryover of drug exposure from the previous dose. There are appropriately named “test” and “reference” study treatments, which will be evaluated for the relative BA comparisons.

This study is participant to the appropriate regulatory and ethics committee approval and will be listed on the website ClinicalTrials.gov. No blinding or placebo control will be used, as these are not necessary for the purposes of this study.

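### Do the Part 2 precision tables mislead by stopping at a food effect of 1.2 and relying on a CVw of 38% seen only with moderate-fat meals?

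*Protocol*

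**What the plan says.** Section 9.2.1 of the Protocol takes its variability from earlier studies. The within-subject CV was 17% to 38% for AUC and 13% to 31% for Cmax in Studies 207187 and 208131, and 7.8% and 11.5% in Study 209712. From these, "it is decided that 38% would be a conservative estimate on which the sample size calculation is based".

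For Part 2 the section states: "Administration of GSK3640254 with a high fat meal compared to fasting is expected to increase the exposure to GSK3640254". It then adds: "therefore, a range for PE of 1.0, 1.1, and 1.2 was explored". Section 9.2.2 keeps the same three ratios and varies CVw from 10% to 40%.

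The only quantitative food-effect evidence is in Section 4.2 and concerns the structurally similar GSK3532795: "AUC increased 1.8-, 2.1-, and 2.5-fold when a single dose of 180 mg GSK3532795 was given with a light, moderate, or high fat meal", against fasting. For GSK3640254 itself, Section 2.1 says that all completed studies "have been conducted with moderate calorie and fat meals".

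Section 9.1 says that no formal hypothesis will be tested and that the sample size rests on feasibility. Section 9.4.1 specifies a mixed model on log-transformed AUC and Cmax, with 90% CIs exponentiated to geometric mean ratios.

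**The concern.** The protocol describes a related compound whose AUC rose 2.1-fold with a moderate-fat meal and 2.5-fold with a high-fat meal, then tabulates food effects no larger than 1.2. Even the light-meal figure of 1.8 lies outside that range. A reader who expects a large effect finds no row for it, and intervals around 2.1 or 2.5 are visibly wider on the ratio scale than those printed.

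The second strand is the CVw. Fasted dosing is the reference for both Part 2 comparisons, yet every study behind the 38% was dosed with a moderate-fat meal. Calling 38% conservative is therefore not demonstrated for fasted or high-fat dosing, and the sensitivity table reaches only two points higher.

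The stakes would be a false impression of what 16 participants can show in a study intended to be the only food-effect study of this drug. A similar remark could be made about Part 1, which explores 0.9 to 1.1, whereas the relative bioavailability at the previous formulation change "was 112% and 116% based on AUC(0-t) and Cmax, respectively".

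**Working it through.** **Inputs.** Evaluable participants: 14 in Part 1 and 16 in Part 2; CVw 38%; tabulated ratios (all Section 9.2.1). Two-sided 90% CI on the log scale (Section 9.4.1). Analogue ratios 2.1 and 2.5 (Section 4.2). A fasted CVw of 50% or 60% is an assumption, used only to show a range.

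**Formulas.** σ = √ln(1 + CVw²). Log half-width h = t(0.95, df) × σ × √(2/n). CI = ratio × exp(±h). At CVw 38%, σ = √ln(1.1444) = 0.3673.

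**The plan's own figures**
- Part 1, n = 14, df = 13: h = 1.7709 × 0.3673 × 0.3780 = 0.246, and exp(0.246) − 1 = 0.279. Both agree with the table.
- Part 2, n = 16, df = 15: h = 1.7531 × 0.3673 × 0.3536 = 0.228. At a ratio of 1.2 this gives 0.956 to 1.507, against the printed 0.956 to 1.506. The printed CIs are therefore right for the ratios they state.
- The printed Part 2 half-widths, 0.236 and 0.266, match n = 15, df = 14 (1.7613 × 0.3673 × 0.3651 = 0.236). They disagree slightly with the CIs beside them. This is a separate clerical slip of about 0.008 on the log scale, on the wide side.

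**Larger ratios, CVw 38%, n = 16, df = 15.** exp(−0.2276) = 0.796 and exp(0.2276) = 1.256.

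| Ratio | 90% CI | Lower limit | Upper limit |
|---|---|---|---|
| 1.0 | 0.80 to 1.26 | −20% | +26% |
| 1.2 | 0.96 to 1.51 | −20% | +26% |
| 2.1 | 1.67 to 2.64 | −20% | +26% |
| 2.5 | 1.99 to 3.14 | −20% | +26% |

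In absolute terms the interval at 2.1 has width 2.637 − 1.672 = 0.965, against 1.506 − 0.956 = 0.550 printed at 1.2, a factor of 1.75. That factor is simply 2.1/1.2. The printed 0.266 is a multiplicative margin, exp(0.236) − 1, so it should not be set against an absolute distance such as 3.14 − 2.50 = 0.64.

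**Larger CVw, n = 16, df = 15**
- Fed 38%, fasted 50%: h = 1.7531 × √[(0.1349 + 0.2231)/16] = 0.262. At 2.1 the CI is 1.62 to 2.73.
- Fed 38%, fasted 60%: h = 1.7531 × √[(0.1349 + 0.3075)/16] = 0.291. At 2.1 the CI is 1.57 to 2.81.
- 60% in both conditions, a harsher assumption than raised fasted variability alone: h = 0.344. At 2.1 the CI is 1.49 to 2.96.

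If the analogue's effect carried over, every one of these intervals would lie well above 1.

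**Part 1 at a ratio of 1.16.** The CI is 0.907 to 1.483, against the printed 0.860 to 1.407 at 1.10.

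**The case for a change.** The best case for a change is that the precision tables are the only account of what the trial can deliver. With no hypothesis and a feasibility-based sample size, they should at least cover the range that the protocol itself makes plausible. Section 4.2 treats the related compound as relevant and Section 9.2 passes over it without a reason. Section 9.2.1 also says that a sample size calculation rests on the 38%, which sits awkwardly with Section 9.1. Adding rows would cost almost nothing.

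Part of this stands. The tabulated ratios do not span the analogue's effect, and the 38% is conservative only relative to the moderate-fat data cited. The strand about variability has more substance than the strand about ratios, because CVw does change relative precision.

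The rest is weaker. The 2.1 and 2.5 are AUC ratios for a different compound at 180 mg, and the protocol projects no fold-change for GSK3640254. Nothing in the document indicates that fasted CVw exceeds 38%, which is already the top of the observed range, well above the most recent study. The 1.12 and 1.16 relevant to Part 1 came from a change of salt between two capsules, whereas Part 1 compares a tablet with a capsule of the same salt.

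**Conclusion.** The observation is accurate but leads nowhere. Relative precision is the same at any ratio, so a reader can scale the tabulated half-width to 2.1 or 2.5 with one multiplication. The tables support no power claim, equivalence limit or decision threshold, and the sample size does not come from them. The reported intervals will use the variability seen in the trial, so an optimistic planning CVw would not make them falsely narrow.

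If fasted variability did prove higher, the log half-width would move from 0.228 to about 0.262 to 0.291 (assuming a fasted CVw of 50% to 60% and a fed CVw of 38%), a loss that leaves a food effect of the analogue's size plainly visible. Adding larger ratios or CVw rows would be a courtesy to the reader with no gain for the trial, so no change to the plan is called for. This conclusion rests on the sample size staying feasibility-based and on the analysis staying on the log scale, both as the protocol states. The mismatch between printed half-widths and CIs in Part 2 is a different, clerical matter and does not alter it.

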9.2.2. Sample Size Sensitivity

For a sensitivity analysis, assuming a range of within-subject variability, a sample size of 14 evaluable subjects for Part 1 and a sample size of 16 evaluable subjects for Part 2, it is estimated that the precision (i.e. half-width of the 90% CI on the log and ratio scale), and CI on the original scale for each PE will be:

Comparison	CVw (%)	Half-Width (log scale)	Half-Width (original scale)	Point Estimate	90% CI
Tablet to capsule	10	0.067	0.069	0.9	(0.842, 0.962)
				1.0	(0.935, 1.069)
				1.1	(1.029, 1.176)
	20	0.133	0.142	0.9	(0.788, 1.028)
				1.0	(0.875, 1.142)
				1.1	(0.963, 1.256)
	30	0.196	0.217	0.9	(0.740, 1.095)
				1.0	(0.822, 1.217)
				1.1	(0.904, 1.338)
	40	0.258	0.294	0.9	(0.695, 1.165)
				1.0	(0.773, 1.294)
				1.1	(0.850, 1.424)

Comparison	CVw (%)	Half-Width (log scale)	Half-Width (original scale)	Point Estimate	90% CI
Fasted to fed	10	0.064	0.066	1.0	(0.940, 1.064)
				1.1	(1.034, 1.170)
				1.2	(1.128, 1.277)
	20	0.127	0.135	1.0	(0.884, 1.131)
				1.1	(0.973, 1.244)
				1.2	(1.061, 1.357)
	30	0.189	0.208	1.0	(0.834, 1.200)
				1.1	(0.917, 1.320)
				1.2	(1.000, 1.440)
	40	0.248	0.281	1.0	(0.787, 1.270)
				1.1	(0.866, 1.397)
				1.2	(0.945, 1.524)

In Part 1, approximately 18 participants will be treated to ensure that 14 evaluable participants complete the study. In Part 2, approximately 21 participants will be treated to ensure that 16 evaluable participants complete the study. If participants prematurely discontinue the study, additional participants may be randomized after consultation with the sponsor to ensure that the required number of evaluable participants complete the study.

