Primary	
 • The primary endpoints of this study are PK-related. The analysis for the primary PK endpoints will be performed for the PK Parameter Population. Plasma concentrations of GSK3640254 will be subjected to PK analyses using noncompartmental methods. • Based on the individual concentration-time data the following primary plasma PK parameters will be estimated: 
 ○ AUC(0-∞), AUC(0-t), Cmax, and Tmax • Analysis will be performed to compare the relative BA of a tablet formulation of GSK3640254 with the capsule formulation, as appropriate. Analyses will be performed on the natural logarithms of AUC(0-∞), AUC(0-t), and Cmax using linear mixed-effect models with treatment, period, and sequence as fixed effects and participant as a random effect. Effects will be estimated, and CIs will be constructed for the following treatment comparison: 
 ○ Treatment B (test) versus Treatment A (reference) 
Point estimates and 90% CIs for treatment differences on the log scale derived from the model will be exponentiated to obtain estimates for geometric mean ratios and CIs on the original scale.
 • The effect of food (moderate or high fat meal) on the PK of the tablet formulation of GSK3640254 will be similarly analyzed for the following treatment comparisons: 
 ○ Treatment C (test) versus Treatment D (reference) ○ Treatment E (test) versus Treatment D (reference) • Non-parametric analysis will be performed to compare the Tmax of a tablet formulation of GSK3640254 with the capsule formulation, as appropriate. The Hodges-Lehmann estimate will be used to produce the median, median difference, and 90% CIs for the following comparison: 
 ○ Treatment B (test) versus Treatment A (reference) 
A p-value will be generated by the Wilcoxon signed-rank test.
 • The effect of food (moderate or high fat meal) on the Tmax of the tablet formulation of GSK3640254 will be similarly analyzed for the following comparisons: 
 ○ Treatment C (test) versus Treatment D (reference) ○ Treatment E (test) versus Treatment D (reference) • Summary statistics (arithmetic mean, geometric mean, median, standard deviation, minimum, maximum, and coefficient of variation) for plasma GSK3640254 primary PK parameter values will be summarized by treatment.

Endpoint	Statistical Analysis Methods

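### In every Part 2 row of the precision tables (Protocol 9.2.1 and 9.2.2) the stated half-width disagrees with the 90% CIs beside it and with 16 evaluable subjects

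*Protocol*

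**What the plan says.** Section 9.2.1 sets out the expected precision "with a sample size of 14 evaluable subjects in Part 1 and a sample size of 16 evaluable subjects in Part 2". For Part 2 the lead-in to its table reads "a sample size of 16 evaluable subjects in Part 2, it is estimated that the precision (i.e. half-width of the 90% CI", and the half-width is given on the log and ratio scales. Its Part 2 row at the conservative CVw of 38% begins "GSK3640254 high fat to fasted 38 0.236 0.266 1.0 (0.797, 1.255".

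Section 9.2.2 repeats this for CVw of 10, 20, 30 and 40%, again assuming "a sample size of 14 evaluable subjects for Part 1 and a sample size of 16 evaluable subjects for Part 2". The first Part 2 row there begins "Fasted to fed 10 0.064 0.066 1.0 (0.940, 1.064" and the last begins "40 0.248 0.281 1.0 (0.787, 1.270".

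Section 9.1 says that no formal hypothesis is tested and that "the sample size is not selected based on statistical considerations but was determined using feasibility". Section 9.4.1 plans point estimates and 90% CIs for the food-effect comparisons, including "Treatment E (test) versus Treatment D (reference".

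**The concern.** A half-width and a confidence interval in the same row describe the same quantity. With a point estimate of 1.0, the upper limit has to equal 1 plus the ratio-scale half-width. This holds in all five Part 1 rows (for example 0.279 and 1.279) and fails in all five Part 2 rows (for example 0.266 and 1.255). Each Part 2 row therefore states two different precisions for one sample size.

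Because the study tests no hypothesis, these tables are where the protocol says what 16 evaluable subjects will deliver. A colleague checking the design from the half-width column would not arrive at 16, and the wrong figures could be carried into later documents.

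**Working it through.** **Inputs.** Evaluable subjects: 14 in Part 1 and 16 in Part 2 (Sections 9.2.1 and 9.2.2). Two-sided 90% CI, so the 0.95 quantile. CVw 38% (9.2.1) and 10, 20, 30, 40% (9.2.2). The protocol does not state the degrees of freedom, so they are inferred from Part 1.

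**Formulas.**
- σw = √ln(1 + CVw²)
- log half-width h = t(0.95, n−1) · σw · √(2/n)
- ratio-scale half-width = exp(h) − 1
- CI = PE · exp(±h)
- half-width implied by a printed CI = ln(upper/lower)/2

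**Step 1: reproduce Part 1 (n=14, df 13).**

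| CVw | Computed h | Printed h |
|---|---|---|
| 38% | 0.2458 | 0.246 |
| 10% | 0.0668 | 0.067 |
| 20% | 0.1326 | 0.133 |
| 30% | 0.1965 | 0.196 |
| 40% | 0.2579 | 0.258 |

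All five agree to within 0.001, so this is the tables' own convention.

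**Step 2: Part 2 half-widths against their own CIs and against n=16 (df 15).**

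| CVw | Printed h (log/ratio) | Implied by printed CI at PE 1.0 | Computed, n=16 (log/ratio) |
|---|---|---|---|
| 38% | 0.236 / 0.266 | 0.2270 | 0.2276 / 0.2556 |
| 10% | 0.064 / 0.066 | 0.0620 | 0.0618 / 0.0638 |
| 20% | 0.127 / 0.135 | 0.1232 | 0.1227 / 0.1306 |
| 30% | 0.189 / 0.208 | 0.1819 | 0.1819 / 0.1996 |
| 40% | 0.248 / 0.281 | 0.2393 | 0.2388 / 0.2697 |

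The printed log half-widths exceed the n=16 values by about 3.5% to 3.9% (for example 0.236/0.2276 = 1.037).

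**Step 3: CIs that the printed half-widths would give at PE 1.0.**

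| CVw | From printed h | Printed CI |
|---|---|---|
| 38% | (0.790, 1.266) | (0.797, 1.255) |
| 10% | (0.938, 1.066) | (0.940, 1.064) |
| 20% | (0.881, 1.135) | (0.884, 1.131) |
| 30% | (0.828, 1.208) | (0.834, 1.200) |
| 40% | (0.780, 1.281) | (0.787, 1.270) |

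**Step 4: can rounding explain it?** Allowing ±0.0005 on each printed limit, the CIs at PE 1.0 permit log half-widths of 0.2265–0.2275, 0.0615–0.0625, 0.1227–0.1237, 0.1814–0.1824 and 0.2388–0.2398 (CVw 38, 10, 20, 30, 40%). Every printed half-width lies outside its range.

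**Step 5: can another choice of df explain it?** At n=16 and CVw 38%, df of 13, 14, 15, 28 and 30 and the normal quantile give 0.214 to 0.230, never 0.236.

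**Step 6: what do the printed half-widths fit?** With n=15 and df 14 the formula gives 0.2362, 0.0642, 0.1274, 0.1888 and 0.2478, which match. With n=14 and df 28 it gives 0.2361, 0.0641, 0.1273, 0.1887 and 0.2477, which also match. The cause cannot be settled from the protocol.

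**Step 7: which column is right?** Of the 15 printed Part 2 CIs, 10 are unchanged to three decimals when recomputed at n=16, df 15; the other five (the three at 38%, 30% at PE 1.2, and 40% at PE 1.0) move by 0.001. The CI column belongs to 16 subjects and the half-width columns do not.

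**The case against.** The mismatch itself is hard to dispute; the case on the other side is about weight and about how firm the replacement figures are.

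- **Weight.** No decision rule, margin or enrolment target uses the half-width. The CIs, which most readers would use, are already right to about 0.001. The error understates precision, and at a CVw of 10% the gap is only 0.064 against 0.062. All of this stands, and it limits the importance of the point.
- **Degrees of freedom.** The replacement values rest on df = n−1, which the protocol never states. If the Part 2 mixed model were fitted to all three treatments with complete data on 16 subjects, the within-subject residual df would be 48 − 1 − 15 − 2 − 2 = 28, and the half-width at 38% would be 0.221 (ratio 0.247). With 14 df it would be 0.229 (0.257). This is fair: the figures proposed here are right under the tables' own convention, and that condition should be stated. It does not rescue 0.236, which lies further from all of these values.
- **Small CI changes.** Shifts of 0.001 come from rounding the half-width before forming the interval and are not errors of substance. That also stands; refreshing the CIs is housekeeping.

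**Conclusion.** The tables are wrong as written. That the half-widths and CIs conflict in all five Part 2 rows follows from the definition of a half-width and needs no assumption about method. That the half-widths are the faulty entries rests on one assumption: Part 2 was meant to follow the formula that reproduces Part 1, with n−1 degrees of freedom. Under it, the Part 2 half-widths are about 4% too wide (0.236 against 0.228 at CVw 38%) and the CIs are off by at most 0.001. A calculation with 15 subjects is a likely source but is not proven.

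The practical effect is small. The error is on the conservative side, and with the sample size set by feasibility neither enrolment nor analysis changes. The correction should nevertheless be made.

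**What to change.** In the Part 2 rows of the tables in Sections 9.2.1 and 9.2.2, replace the two half-width columns with the n=16 values, and add a note giving the formula and the degrees of freedom (n−1):

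| CVw | Log scale | Ratio scale |
|---|---|---|
| 38% | 0.228 | 0.256 |
| 10% | 0.062 | 0.064 |
| 20% | 0.123 | 0.131 |
| 30% | 0.182 | 0.200 |
| 40% | 0.239 | 0.270 |

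For consistency, take the Part 2 CIs from the same unrounded calculation. The 38% row becomes (0.796, 1.256), (0.876, 1.381) and (0.956, 1.507) for PE 1.0, 1.1 and 1.2. In the sensitivity table, 30% at PE 1.2 becomes (1.000, 1.439) and 40% at PE 1.0 becomes (0.788, 1.270). If the sponsor intends other degrees of freedom for Part 2, both columns should be recomputed with them.

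As an optional tidy-up, the row label in Section 9.2.2 could read fed to fasted, since Sections 9.2.1 and 9.4.1 treat fasted as the reference.

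The cost is an edit to two tables, with no change to enrolment, procedures or analysis.
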